4.3 JUSTIFICATION FOR DOSE

The concentration of dexamethasone (1 mg/ml) and dose (1 drop, 4 times a day) in both the test and standard combinations is well established in ophthalmic solutions, both as sole active ingredient or in combination with an antibiotic. Levofloxacin is also well established as sole active ingredient of ophthalmic solutions at a concentration of 5 mg/ml and at a dose of 1 drop, 4 times a day.

Tobradex[®] will be administered as per label.

4.4 END OF STUDY DEFINITION

A participant is considered as having completed the study if he or she has completed all phases of the study including the last visit as indicated in the Schedule of Activities (SoA), *Section 1.3*.

The end of the study is defined as completion of the last visit as shown in the SoA in the trial globally.

5 STUDY POPULATION

5.1 INCLUSION CRITERIA

To be eligible to participate in this study, a subject must meet all the following criteria:

5.1.1 INCLUSION CRITERIA PRIOR TO SURGERY

- 1. Signed written informed consent must be obtained before any assessment is performed
- 2. Male or female, age ≥ 40 years
- 3. Scheduled senile or presenile cataract surgery (not yet performed).
- 4. Willing to interrupt the use of contact lenses for the entire duration of the study

- 5. Able and willing to follow study procedures
- 6. Female patients must be postmenopausal (24 months of amenorrhea), surgically sterile or must agree to use an effective method of contraception, which include an established hormonal therapy or intrauterine device for females, and the use of a barrier contraceptive (i.e. diaphragm or condoms) with spermicide.

5.1.2 INCLUSION CRITERIA FOLLOWING SURGERY

7. Surgery completed without complications

5.2 EXCLUSION CRITERIA

An individual who meets any of the following criteria will be excluded from participation in this study:

- 1. Ocular conditions that at the discretion of the Investigator may interfere with the efficacy and/or safety evaluations (e.g. ocular herpes, blepharitis, conjunctivitis, uveitis, keratitis, diabetic retinopathy, retinal vein occlusions, retinal vasculitis, retinal angiomatous proliferation, pseudoexfoliation syndrome, intraoperative floppy iris syndrome, etc.)
- 2. Patients undergoing bilateral cataract surgery
- 3. Patients under treatment with prostaglandin analogues or intravitreal injections of anti-VEGF (vascular endothelial growth factor) drugs
- 4. Systemic diseases that may interfere with the results of the study (e.g. rheumatoid arthritis, Sjögren's syndrome, Behçet's disease, systemic lupus erythematosus, scleroderma with major ocular involvement, etc.)
- 5. Any condition that could interfere with correct instillation of eye drops
- 6. Ocular surgery in the study eye (including laser surgery) in the 3 months before screening
- 7. Monocular patients
- 8. Visual Acuity (VA) < 20/80 of the contralateral eye measured as ETDRS or Snellen 20 feet, equal to 0.25 in decimal
- 9. Contraindications to ocular treatment with Tobradex[®], Maxidex[®] or levofloxacin/dexamethasone as follows:
 - Herpes simplex keratitis, vaccinia, varicella and other viral diseases of the cornea and conjunctiva
 - Fungal and mycobacterial diseases of ocular structures or untreated parasitic eye infections
 - Uncontrolled intraocular hypertension
 - Uncontrolled glaucoma

Tobradex[®] is contraindicated also in case of untreated purulent infection of the eye, whereas Maxidex[®] is contraindicated in acute, untreated bacterial infections.

10. Hypersensitivity to the study product or its excipients

- 11. Participation in other clinical studies if at least 5 half-lives of the IMP used in the previous studies have not passed between the end of treatment in the previous study and the start of treatment in this clinical study.
- 12. Pregnancy or breastfeeding

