2 INTRODUCTION

2.1 STUDY RATIONALE

In clinical practice, topical treatment following cataract surgery is frequently administered using a combination between an antibiotic and a corticosteroid to promote patient adherence to therapy and to obtain both the prevention of infection and the treatment of post-surgical inflammation. The combination of tobramycin and dexamethasone is among the most widely used combinations, but treatment usually lasts for two or more weeks, sometimes tapering posology over several weeks. This therapeutic strategy may however be inappropriate in terms of preventing the development of bacterial resistance, which is favored by prolonged treatment and the use of sub-therapeutic doses. For this reason, antibiotic treatment should not be prolonged beyond the time necessary for the healing of surgically induced epithelial lesions, and therefore should not last more than a week.

Based on these considerations, a product associating a broad-spectrum antibiotic with a highly effective corticosteroid that can be used for a short period of time (one week) would be of considerable interest.

The combination of levofloxacin and dexamethasone tested in this study is the first combination of a quinolone and a steroid under development and represents a major step forward in this direction. Levofloxacin 0.5% + dexamethasone 0.1% ophthalmic solution is an antibiotic/anti-inflammatory combination indicated for the treatment of inflammatory ocular conditions, where bacterial ocular infection or a risk of bacterial ocular infection exists. The active components of this combination are currently available in marketed ophthalmic products.

The purpose of this study is to evaluate the efficacy of a combination between levofloxacin and dexamethasone by demonstrating that the short-term use of this combination for a limited time of one week, followed by treatment with dexamethasone alone, is not inferior to longer treatment with tobramycin + dexamethasone in reducing the incidence of post-operative inflammation/infections while limiting emergence of antibiotic resistance.

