6.5.1 PROHIBITED CONCOMITANT THERAPY

The following treatments are not permitted:

- Topical antibiotics
- Systemic antibiotics for prophylactic purposes
- Topical or systemic steroids

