12 APPENDICES

APPENDIX 1: TOTAL OCULAR SYMPTOMS SCORE (TOSS)

TOSS Questionnaire

Please answer the following questions by marking the box that best represents your answer:

Have you experienced any of the following, and if so with what intensity?	None	Mild	Moderate	Severe
1. Itching/burning?				
2. Redness?				
3. Tearing (eyes watering)?				

TOSS Questionnaire Scoring

Total Ocular Symptom Score

1. Add up scores for the three symptoms.

None = 0

Mild = 1

Moderate = 2

Severe = 3

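### The TOSS form and the pain/discomfort item do not name the operated eye, and the eligibility rules do not clearly keep other-eye symptoms out of these secondary endpoints

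*Combined protocol and SAP*

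**What the plan says.** **The patient-reported items.** The Appendix 1 questionnaire opens with "Have you experienced any of the following, and if so with what intensity" and lists itching/burning, redness and tearing. The tearing item uses the plural, eyes. Section 8.2 repeats the three symptoms without naming an eye, and has the patient rate overall pain and discomfort from 0 to 3. Section 9.4.3 analyses both measures as the proportion of patients scoring 0 after 3, 7 and 14 days.

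**The eligibility rules (section 5.2).**
- Criterion 6 excludes "Ocular surgery in the study eye (including laser surgery) in the 3 months before screening".
- Criterion 2 excludes "Patients undergoing bilateral cataract surgery", with no time window and no definition.
- The only explicit rules on the other eye are the exclusion of monocular patients and criterion 8: "Visual Acuity (VA) < 20/80 of the contralateral eye measured as ETDRS or Snellen 20 feet, equal to 0.25 in decimal".
- Criterion 1 leaves to the investigator "Ocular conditions that at the discretion of the Investigator may interfere with the efficacy and/or safety evaluations". Recent surgery on the other eye is not among its examples.

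**The treatment ban (section 6.5.1).** The list includes "Topical antibiotics" and "Topical or systemic steroids". It names no eye and no start date, and no exclusion criterion refers to it.

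**The concern.** A patient completing the TOSS form is asked about symptoms in general. If the other eye itches, is red or waters, a literal answer puts that symptom into the score. Recent surgery on that eye is an obvious possible cause, but any cause will do. Because success means a score of exactly 0, one mild symptom in the eye that received no study drug turns a success into a failure.

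Such failures carry no information about the assigned drops. They should occur about equally in both arms, so they pull the arms together rather than favour one. In a trial built to show similarity, supporting endpoints that are pushed toward no difference deserve attention even when they carry no formal test.

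The eligibility text could have made this unimportant by keeping out patients with a recently treated other eye. It does not do so clearly, and about 80 centres in four countries are left to settle the reading for themselves.

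**Working it through.** The plan gives no figure on this point to reproduce. The sample size of 362 per group rests on the primary endpoint alone and is not touched. The check is a reading of the passages against each other, plus one line of algebra.

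**Step 1: how easily is a 0 lost?** TOSS adds three items scored 0 to 3, so it runs from 0 to 3 × 3 = 9. Success needs 0 + 0 + 0. One mild symptom gives 1 and is a failure. The pain/discomfort item is a single 0 to 3 rating, so any rating above 0 is a failure.

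**Step 2: can a patient with a recently operated other eye be enrolled?** Take a patient whose other cataract was removed some weeks before screening.

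| Rule | Result |
|---|---|
| Criterion 6 | Does not apply; it is limited to the study eye |
| Criterion 2, read as one session | Not excluded |
| Criterion 2, read as including sequential surgery | Excluded |
| Criterion 8 | Passed if the other eye sees at least 20/80 |
| Criterion 1 | Depends on the investigator |

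The answer turns on a word the protocol does not define. For laser or other non-cataract surgery on the other eye, criterion 2 does not apply on either reading, because it concerns cataract surgery only.

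**Step 3: is the treatment ban aligned with eligibility?** Section 2.1 says of tobramycin/dexamethasone after cataract surgery that "treatment usually lasts for two or more weeks, sometimes tapering posology over several weeks". A patient admitted on the one-session reading could therefore still be using such drops in the other eye. Section 6.5.1, taken literally, prohibits that use. Section 8.1 has concomitant medications recorded on the day of surgery, but the only ones it says are to be stopped are prophylactic pre-operative medications. So a patient may satisfy the listed criteria and still be in breach of 6.5.1 at randomisation. Section 9.3 removes significant violations from the per-protocol set. It does not say whether drops in the other eye would count as one.

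**Step 4: direction of the effect.** Let p_T and p_S be the true proportions scoring 0 for the operated eye. Let f be the fraction of patients who score above 0 because of the other eye, whatever the operated eye does. Assume f is the same in both arms (randomisation gives this on average) and is unrelated to the operated eye's outcome. Then

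- observed proportion, test arm: (1 − f) p_T
- observed proportion, control arm: (1 − f) p_S
- observed difference: (1 − f)(p_T − p_S)

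Any true difference shrinks toward 0 by the factor 1 − f. Nothing in the documents fixes f.

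**Step 5: reach.** The primary endpoint is a slit-lamp score of cells and flare, analysed on the full analysis set. The other eye's symptoms do not enter that score. Section 2.2 also describes plasma concentrations of topical levofloxacin and dexamethasone as negligible, so drops in the other eye give no evident route to the study eye's inflammation score.

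**The case against.** The strongest reply is that this does not bear on the trial's conclusion, and that is right. TOSS and pain are secondary, section 9.1 plans no formal test of them, and section 9.4.3 gives only descriptive statistics and confidence intervals. Randomisation is 1:1 and stratified by centre, so no bias toward one arm has been shown.

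It can also be said that the protocol has safeguards: criterion 2 on its wider reading, the discretion in criterion 1, the recheck of criteria on the day of surgery, and a ban in 6.5.1 that is not confined to one eye. These narrow the gap but do not close it. None of them changes what the questionnaire asks.

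Three stronger inferences are tempting, and the documents do not support them.

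- *Patients with a recently operated other eye are definitely admitted.* This holds only on one reading of criterion 2.
- *The per-protocol set would lose so many patients that power suffers.* The documents give no rate of other-eye surgery or drop use, and do not say that other-eye drops remove a patient from that set. The set is supportive only.
- *One person could be entered twice and counted as two.* Section 8.1 gives each patient a unique number that is not reused. Re-entry is not expressly barred, but nothing suggests that it is intended or likely.

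**Conclusion.** The concern holds as a gap in measurement wording, with an eligibility text that does not reliably compensate for it. Used as written, the TOSS form and the pain/discomfort item can record symptoms of the eye that received no study treatment, and the score-of-0 definition makes both endpoints sensitive to a single mild symptom. The consequence is dilution of any arm difference by the factor 1 − f, under the assumption that other-eye symptoms are equally frequent in both arms and unrelated to the operated eye's course.

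The size cannot be given, because the documents contain no rate of other-eye symptoms or surgery. The reach is limited to these patient-reported secondary endpoints and possibly to who belongs to the supportive per-protocol set. This is a low-cost improvement, not a threat to the non-inferiority conclusion.

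**What to change.** 1. Add *in the operated eye* to the TOSS stem and to the pain/discomfort item, and put the tearing item in the singular. Carry the same wording into section 8.2. The cost is a small change to the questionnaire and its translations.
2. Reconcile criteria 2 and 6 with section 6.5.1, so that every site applies one reading of bilateral and of which eye the medication ban covers, and from when. State in section 9.3 how a departure on the other eye affects per-protocol membership. The cost is a few lines of text.
3. Leave to the sponsor whether to set any window for surgery on the other eye. Extending criterion 6 to both eyes would trade eligible patients for cleaner symptom data, and the documents do not give the figures to judge that trade. Item 1 removes most of the measurement problem without it.

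No change to the sample size or to the primary analysis is needed.

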The main purpose of this amendment is to address concerns raised during review of the study protocol by regulatory authorities (BfArM) regarding inclusion/exclusion criteria and the conditions requiring temporary interruption or permanent discontinuation of study treatments. The following changes to the protocol have been made in light of these requests:

- Inclusion criterion 3 was modified to clarify that the study will enroll patients scheduled for cataract surgery (not yet performed) (*Section 5.1*). The criterion has been split into two, one indicating the inclusion of patients scheduled for surgery (not yet performed), and the other stating that only patients who completed surgery without complications will be randomized.
- Exclusion criterion 9, which previously referred to contraindications to ocular treatment with levofloxacin, tobramycin or dexamethasone in general terms, now indicates all the specific contraindications to study treatments as stated in their respective Summary of Product Characteristics (SPC) or Investigator's Brochure (IB) (*Section 5.2*). Since the warnings and precautions related to study treatments apply to situations that may arise following screening, a sub-section has been added to the treatment section of the protocol listing all the warnings and precautions as per SPC or IB (*Section 6.6*). Specific situations requiring study treatment discontinuation according to SPC or IB have been added to *Section 7.1*.
- Exclusion Criterion 11 now states that participation in previous clinical studies is possible if at least 5 half-lives of the IMP used in the previous studies have passed between the end of treatment in the previous study and the start of treatment in this clinical study.
- The amendment now states that temporary interruption of study treatment and dose modifications are not foreseen in the protocol (*Section 7.1*). Additional information has also been added indicating the conditions for permanent discontinuation.

The amended protocol also clarifies that testing of visual acuity is to be performed according to local practice. Minimum visual acuity of the contralateral eye required for study entry (Exclusion criteria 8) has consequently been converted and is now stated using various standards (*Section* 5.2).

Changes to specific sections of the protocol are shown in the track changes version of the protocol using strike through red font for deletions and red underline for insertions.

STATEMENT OF COMPLIANCE

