Exclusion criteria	 Surgery completed without complications Ocular conditions that at the discretion of the Investigator may interfere with the efficacy and/or safety evaluations (e.g. ocular herpes, blepharitis, conjunctivitis, uveitis, keratitis, diabetic retinopathy, retinal vein occlusions, retinal vasculitis, retinal angiomatous proliferation, pseudoexfoliation syndrome, intraoperative floppy iris syndrome, etc.) Patients undergoing bilateral cataract surgery Patients under treatment with prostaglandin analogues or intravitreal injections of anti-VEGF (vascular endothelial growth factor) drugs Systemic diseases that may interfere with the results of the study (e.g. rheumatoid arthritis, Sjögren's syndrome, Behçet's disease, systemic lupus erythematosus, scleroderma with major ocular involvement, etc.) Any condition that could interfere with correct instillation of eye drops Ocular surgery in the study eye (including laser surgery) in the 3 months before screening Monocular patients Visual Acuity (VA) < 20/80 of the contralateral eye measured as ETDRS or Snellen 20 feet, equal to 0.25 in decimal Contraindication to ocular treatment with Tobradex®, Maxidex® or levofloxacin/dexamethasone as follows: Herpes simplex keratitis, vaccinia, varicella and other viral diseases of the cornea and conjunctiva Fungal and mycobacterial diseases of ocular structures or untreated parasitic eye infections Uncontrolled intraocular hypertension Uncontrolled glaucoma Tobradex[®] is contraindicated also in case of untreated purulent infections of the eye, whereas Maxidex[®] is contraindicated in acute, untreated bacterial infections.
	 Hypersensitivity to the products or their excipients Participation in other clinical studies if at least 5 half-lives of the IMP used in the previous studies have not passed between the end of treatment in the previous study and the start of treatment in this clinical study.

	12. Pregnancy or breastfeeding

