2.3 RISK/BENEFIT ASSESSMENT

2.3.1 KNOWN POTENTIAL RISKS

In toxicity studies, the only toxicity data reported for dexamethasone were those related to an exaggerated pharmacological activity including a negative feedback on the pituitary-adrenal axis. Systemic effects are however not expected or are negligible when the drug is topically administered as eye drops and for a limited period. Nevertheless, its potential effect on fetal development and on newborns suggests it be used very carefully in pregnant women and to discard the milk during lactation.^{40,41}

Possible adverse effects of topical ocular corticosteroid therapy include an increase of intraocular pressure (IOP), inhibition of corneal wound healing and increased likelihood of infection and serious complications, but systemic adverse effects are rare.^{9,10}

Levofloxacin is not toxic on reproduction and does not have mutagenic or carcinogenic potential. It is not irritating after eye instillation, but it is phototoxic at very high doses and photosensitization cannot be excluded.^{19,42} Patients should therefore not be exposed to direct sunlight during treatment with eye drops containing levofloxacin.

In clinical studies involving over 1600 patients, no serious ophthalmic or systemic adverse reactions were reported for the combination of tobramycin + dexamethasone (Tobradex[®]), comparator drug for this study. The most frequently reported adverse reactions were eye pain, increased intraocular pressure, eye irritation (burning upon instillation) and eye pruritus occurring in less than 1% of patients.⁴³

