6.1.2 DOSING AND ADMINISTRATION

- ✤ Test arm
 - Levofloxacin + dexamethasone eye drops for 7 days, 1 drop 4 times a day (hours 8.00, 13.00, 18.00 and 23.00 ± 30 minutes), followed by dexamethasone eye drops alone (Maxidex[®]) for an additional 7 days, 1 drop 4 times a day (hours 8.00, 13.00, 18.00 and 23.00 ± 30 minutes).
- ✤ Control arm
 - Tobramycin + dexamethasone eye drops (Tobradex[®]) for 14 days, 1 drop 4 times a day (hours 8.00, 13.00, 18.00 and 23.00 ± 30 minutes).

In both arms, patients will start treatment according to local routine clinical practice, i.e. either immediately after randomization in those patients who are not bandaged after surgery, or soon after removal of dressing of operated eye. Doses administered on the same day as surgery will be considered additional to the full protocol dosage regimen (4 instillations per day for 14 days).

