6.3 MEASURES TO MINIMIZE BIAS: RANDOMIZATION AND BLINDING

This is a randomized, blinded-assessor study. Patients will be assigned to one of the two following treatment groups in 1:1 ratio according to a randomization list stratified by center:

- Test arm: levofloxacin + dexamethasone ophthalmic solution for 7 days followed by dexamethasone ophthalmic suspension (Maxidex[®]) alone for an additional 7 days
- Control arm: tobramycin 3 mg/ml + dexamethasone 1 mg/ml (Tobradex[®]) ophthalmic suspension for 14 days

The randomization numbers will be generated using procedures that ensure that treatment assignment is unbiased. A patient randomization list will be produced using a validated system that automates the assignment of randomization numbers.

Patients who fulfill all inclusion criteria and none of the exclusion criteria will be randomized following surgery via an Interactive Web Response System (IWRS) that will assign the patient a

randomization number linked to a treatment arm. Unblinded staff is to use the IWRS to obtain the study treatment to be given to the patient.

The physician in charge of assessing study parameters will be blinded to treatment assignment (blinded assessor). The blinded assessor will not have access to the randomization page of the eCRF. A separate investigational staff will be unblinded and responsible for assigning and dispensing/return study products. Study treatment will be dispensed upon randomization and on Day 8.

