6.6 WARNINGS AND PRECAUTIONS RELATED TO STUDY TREATMENTS

The warnings and precautions related to the use Tobradex[®], Maxidex[®] and levofloxacin/dexamethasone as stated in their respective SPCs/IB are listed in the tables below:

Tobradex[®]

Both topical corticosteroids and NSAIDs may slow corneal healing. Caution is therefore advised when using topical dexamethasone and topical NSAIDs concomitantly.

Prolonged use of topical ophthalmic corticosteroids (i.e. longer than the maximum duration used in clinical trials [24 days]) may result in ocular hypertension/glaucoma with resultant damage to the optic nerve and reduced visual acuity and visual fields defects. It is advisable that intraocular pressure be checked frequently. The risk of corticosteroid-induced raised intraocular pressure is increased in predisposed patients (e.g. diabetes).

Corticosteroids can reduce resistance to bacterial, viral, fungal, or parasitic infections and promote their development and mask clinical signs of an infection.

Sensitivity to topically administered aminoglycosides may occur in some patients. Severity of hypersensitivity reactions may vary from local effects to generalized reactions such as erythema, itching, urticarial, skin rash, anaphylaxis, anaphylactoid reactions, or bullous reactions. If hypersensitivity develops during use of this medicine, treatment should be discontinued. Cross-hypersensitivity to other aminoglycosides can occur, and the possibility that patients who become sensitized to topical tobramycin may also be sensitive to other topical and/or systemic aminoglycosides should be considered.

Serious adverse reactions including neurotoxicity, ototoxicity and nephrotoxicity have occurred in patients receiving systemic aminoglycoside therapy. Caution is advised when used concomitantly.

Cushing's syndrome and/or adrenal suppression associated with systemic absorption of ocular dexamethasone may occur after intensive or long-term continuous therapy in predisposed patients. In these cases, treatment should be progressively discontinued

Fungal infection should be suspected in patients with persistent corneal ulceration. If fungal infection occurs, corticosteroids therapy should be discontinued.

Prolonged use of antibiotics may result in overgrowth of non-susceptible organisms, including fungi. If superinfection occurs, appropriate therapy should be initiated.

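### Exclusion criterion 10 does not reach a history of allergy to another aminoglycoside, although the protocol warns of cross-hypersensitivity for Tobradex (minor safety improvement)

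*Combined protocol and SAP*

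**What the plan says.** Criterion 10 appears twice. Section 5.2 has "Hypersensitivity to the study product or its excipients" and the synopsis has "Hypersensitivity to the products or their excipients". Neither mentions a drug class.

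Section 6.3 sets the entry rule: "Patients who fulfill all inclusion criteria and none of the exclusion criteria will be randomized following surgery". Allocation is 1:1 between levofloxacin/dexamethasone followed by Maxidex, and Tobradex (tobramycin plus dexamethasone).

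The Tobradex table in section 6.6 says that "Cross-hypersensitivity to other aminoglycosides can occur", and that the possibility that "patients who become sensitized to topical tobramycin may also be sensitive to other topical and/or systemic aminoglycosides should be considered". The same table describes reactions to topical aminoglycosides that range from local effects to anaphylaxis.

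The Amendment 1 summary explains why these warnings sit in the treatment section and not among the eligibility criteria: "Since the warnings and precautions related to study treatments apply to situations that may arise following screening". Section 7.1 requires permanent discontinuation if hypersensitivity to Tobradex occurs.

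**The concern.** A patient may arrive at screening with a documented reaction to an aminoglycoside other than tobramycin. The protocol recognizes that sensitivity can cross within this class, and half of the randomized patients receive a member of it. Yet the eligibility text asks only about the study products and their excipients.

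Amendment 1's reason for placing the warning in section 6.6 is that such situations may arise after screening. An allergy already in the history is not a situation of that kind, so the stated reason does not cover it.

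What is at stake is the safety of a few individual patients. The trial's result is not in question.

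**Working it through.** **1. Does any other exclusion criterion in section 5.2 catch this patient?**

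- Criterion 1 is discretionary but limited to ocular conditions.
- Criterion 4 concerns systemic diseases that could disturb the results; its examples are autoimmune diseases.
- Criterion 5 concerns the ability to instil drops correctly.
- Criterion 9 is a list of contraindications: viral, fungal, mycobacterial and parasitic eye disease, uncontrolled ocular hypertension, uncontrolled glaucoma, and a note on untreated purulent or bacterial infection. Drug allergy is not in it.
- Criterion 10 stops at the products and excipients.
- The remaining criteria (bilateral surgery, certain concurrent treatments, recent ocular surgery, monocular status, visual acuity, other trials, pregnancy) are unrelated.

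So no exclusion criterion applies, and under section 6.3 the patient can be randomized.

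**2. What does the protocol say about cross-reaction?** The first statement in section 6.6 is general. The second runs from sensitization by tobramycin to a reaction to another aminoglycoside. The path that matters here is the reverse: sensitization by another aminoglycoside, then a reaction to tobramycin. The general statement is compatible with that path, but the protocol does not spell it out.

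**3. Exposure of one such patient.**

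- Chance of Tobradex under 1:1 allocation: 1/2.
- Dosing (section 6.1.2): "4 instillations per day for 14 days", with surgery-day doses extra.
- First planned postoperative visit (section 8.1): Day 4, after 3 full days, so 3 × 4 = 12 scheduled instillations.
- Full course: 14 × 4 = 56 scheduled instillations.

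These figures describe exposure, not risk. The documents give neither the frequency of aminoglycoside allergy among cataract patients nor a reaction rate in such patients, so no expected number of events can be calculated.

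**4. Effect on the statistical design.** The plan's 362 per group reproduces:

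n = (1.960 + 0.842)² × 2 × 0.64 × 0.36 / 0.10² = 7.85 × 0.4608 / 0.01 ≈ 362.

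The inputs are the control rate of 0.64, a true difference of 0, the 0.10 margin, one-sided 0.025 and 80% power. A wider criterion acts before randomization and changes none of them. Under section 9.3, a patient who stops treatment counts as a failure. One such patient among 400 controls moves the control rate by 1/400 = 0.25 percentage points, against a margin of 10 points.

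**The case against.** The strongest reply is that nothing is broken. Amendment 1 states that criterion 9 was rewritten, following regulatory review, to give the specific contraindications from the product information. Criterion 10 may therefore follow the labels, with cross-sensitivity correctly placed among the precautions. The labels are not among the documents, so this can be neither confirmed nor refuted. It stands against anyone who might infer that the protocol omits a labelled contraindication; the documents do not support that reading.

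The second reply is that safeguards exist. Medical history is taken at Visit 1, section 4.3 says Tobradex is given according to its label, and investigators have the section 6.6 warning. Additional visits are available. Section 7.1 requires discontinuation for hypersensitivity to Tobradex, and section 7.2 allows withdrawal in the patient's interest. Criterion 10 is not limited to known hypersensitivity, so an investigator who judges a patient cross-sensitive to tobramycin could apply it as it stands. All of this lowers the risk. But each safeguard either depends on individual judgement, at about 80 centers, or acts only once treatment has been assigned.

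The third reply is the Tobradex safety record in section 2.3.1: "In clinical studies involving over 1600 patients, no serious ophthalmic or systemic adverse reactions were reported". That is reassuring for patients in general. The section does not say whether anyone with an aminoglycoside allergy was among those patients, so the record cannot be turned into a risk limit for the patients at issue.

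A reader might also infer from the singular in section 5.2 that criterion 10 does not cover Tobradex at all, particularly as section 6.2.2 uses the term investigational medicinal product for levofloxacin/dexamethasone. The plural in the synopsis, and the naming of all three products in criterion 9, show that this is not the intent. The difference is editorial, but it is worth removing in the same edit.

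**Conclusion.** The point holds as a minor, inexpensive safety improvement to consider. Criterion 10 is narrower than the hazard the protocol itself describes, and by its wording a patient with a history of allergy to another aminoglycoside can be randomized, with a 1 in 2 chance of Tobradex.

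Two assumptions carry it: that cross-hypersensitivity can also run from another aminoglycoside to tobramycin, and that at least an occasional candidate has such a history. The first is a reasonable inference, not a protocol statement. The second cannot be quantified here, and the number is probably small.

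A reader might infer a threat to the trial's conclusion. There is none: sample size, margin and the non-inferiority analysis stay as they are.

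**What to change.** Use one text for criterion 10 in the synopsis and in section 5.2: *Hypersensitivity to levofloxacin/dexamethasone, Maxidex or Tobradex, to any of their excipients, or to any other aminoglycoside.* Leave out the word *known*, which would narrow the present unqualified criterion. Check for such a history within the Visit 1 medical history.

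The sponsor should consider the same extension to other quinolones for the test arm. Section 6.6 mentions hypersensitivity reactions with systemic fluoroquinolones, but it makes no cross-reaction statement like the one for aminoglycosides.

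The cost is one criterion reworded in two places and one question within an existing assessment. The downside is probably a few extra screen failures; the documents give no figure. These patients would be excluded before randomization, so the planned 800 does not change.
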